7.1.2 Non-investigational Products

Not applicable.

7.1.3 Medical Devices

Other non-investigational medical devices may be used in the conduct of this study as part of standard care.

Non-investigational medical devices (eg, syringes, sterile needles), that are commercially available are not usually provided or reimbursed by Amgen (except, for example, if required by local regulation). The investigator will be responsible for obtaining supplies of these devices.

7.1.4 Other Protocol-required Therapies

There are no other protocol-required therapies in this study.

7.1.5 Other Treatment Procedures

During the 28-day screening period, subjects must discontinue from all AD therapies, except for approved moisturizers (see [Section 7.1.7](#)), for at least the 7 consecutive days immediately prior to day 1. During the study, approved moisturizers are allowed to be applied, with the exception of 8 hours prior to any scheduled visit.

Medications and procedures permitted at any time during the study for subjects enrolled in Part A and Part B include:

- Basic skin care (cleansing and bathing), emollients, bleach baths, topical anesthetics, and antihistamines (all for any duration)
- Medications used to treat chronic diseases such as diabetes, hypertension, and asthma

Part A

In Part A of the study, if needed to control intolerable AD symptoms, rescue treatment for AD may be provided at the discretion of the investigator. Rescue is not allowed in the first 4 weeks of Part A. Topical calcineurin inhibitors may be used for rescue, but are to be reserved for problem areas only (eg, face, neck, intertriginous and genital areas). Investigators are to attempt to limit the first step of rescue therapy to topical medications, and escalate to systemic medications only for subjects who do not respond adequately following at least 7 days of topical treatment. If a subject receives rescue treatment with systemic corticosteroids or nonsteroidal systemic immunosuppressive drugs

(eg, cyclosporine, mycophenolate-mofetil, azathioprine), study treatment is to be immediately discontinued.

All subjects are to complete the schedule of study visits and assessments whether or not they complete study treatment or receive rescue treatment for AD.

Part A Rescue Guidance

Subjects who use TCS are to apply medium potency TCS once daily to areas with active lesions. Low potency TCS should be used once daily on areas of thin skin (eg, face, neck, intertriginous, genital areas, areas of skin atrophy) or for areas where continued treatment with medium potency TCS is considered unsafe.

Triamcinolone acetonide 0.1% cream or fluocinolone acetonide 0.025% ointment are recommended as medium potency TCS therapy; hydrocortisone 1% cream is recommended as low potency TCS therapy. After lesions are under control (clear or almost clear), subjects are to switch from medium potency to low potency TCS and treat once daily for 7 days, then cease TCS therapy.

If the lesions return, subjects are to resume treatment with medium potency TCS, and are to use the step-down approach to low potency TCS described above. For lesions that persist or worsen with once daily application of medium potency TCS, subjects may be treated (further rescued) with high or super-high potency TCS, unless higher potency TCS is considered unsafe.

Part B

Additionally, in Part B of the study, subjects are allowed to apply TCS following completion of all day 1 activities. Subjects should bring their containers of TCS to the site at every visit to have the container weighed and the amount of TCS used since the previous visit recorded.

Subjects who use TCS are to apply medium potency TCS once daily to areas with active lesions. Low potency TCS should be used once daily on areas of thin skin (eg, face, neck, intertriginous, genital areas, areas of skin atrophy) or for areas where continued treatment with medium potency TCS is considered unsafe. Triamcinolone acetonide 0.1% cream or fluocinolone acetonide 0.025% ointment are recommended as medium potency TCS therapy; hydrocortisone 1% cream is recommended as low potency TCS therapy. After lesions are under control (clear or almost clear), subjects are to switch from medium potency to low potency TCS and treat once daily for 7 days, then cease TCS therapy.

If the lesions return, subjects are to resume treatment with medium potency TCS, and are to use the step-down approach to low potency TCS described above. For lesions that persist or worsen with once daily application of medium potency TCS, subjects may be treated (rescued) with high or super-high potency TCS, unless higher potency TCS is considered unsafe.

In Part B, after all week 2 activities are completed, if needed to control intolerable symptoms, subjects may receive rescue treatment with any approved AD therapy (see [Section 7.1.7](#) for excluded treatments). If rescue with TCS is necessary, mometasone 0.1% ointment is recommended as a high potency therapy; betamethasone dipropionate 0.05% optimized ointment or clobetasol propionate 0.05% cream are recommended as super-high potency therapy.

If a subject receives rescue treatment with systemic corticosteroids or nonsteroidal systemic immunosuppressive drugs (eg, cyclosporine, mycophenolate-mofetil, azathioprine) they must be discontinued from study treatment. All subjects are to complete the schedule of study visits and assessments whether or not they complete study treatment or receive rescue treatment for AD.

The use of TCI is to be reserved for problem areas (eg, face, neck, intertriginous and genital areas). TCS and TCI are not to be used concomitantly to treat the same affected areas.

7.1.6 Product Complaints

A product complaint is any written, electronic or oral communication that alleges deficiencies related to the identity, quality, durability, reliability, safety, effectiveness, or performance of a drug(s) or device(s) after it is released for distribution to market or clinic by either Amgen or by distributors and partners for whom Amgen manufactures the material.

This includes any drug(s), device(s) or combination product(s) provisioned and/or repackaged/modified by Amgen. Drug(s) or device(s) includes investigational product.

Any product complaint(s) associated with an investigational product(s), non-investigational product(s), device(s), or combination product(s) supplied by Amgen are to be reported according to the instructions provided in the IPIM.

7.1.7 Excluded Treatments, Medical Devices, and/or Procedures During Study Period

The use of other investigational procedures and products while participating in this study is prohibited. The use of biologics, including dupilumab, is prohibited while participating in this study.

Treatment with systemic immunosuppressive/immunomodulating drugs (eg, methotrexate, cyclosporine, azathioprine, mycophenolate-mofetil, tacrolimus, and interferon gamma), Ig and or blood product during the study period is prohibited.

Vaccination with a live or attenuated vaccine is prohibited during the course of the study.

Planned inpatient surgery or hospitalization during the study period is prohibited.

Phototherapy is prohibited during the first 16 weeks of the study.

In Part A of the study, treatment with TCS, TCI, and prescription moisturizers that contain TCS or TCI is prohibited. Non-prescription moisturizers are allowed.

Prescription moisturizers that have the same ingredients as available over-the-counter moisturizers are allowed for use.

In Part B of the study, treatment with TCI, and prescription moisturizers that contain TCS or TCI is prohibited until the week 2 assessments are completed. Non-prescription moisturizers are allowed. Prescription moisturizers that have the same ingredients as available over-the-counter moisturizers are allowed for use. Topical calcineurin inhibitors are only permitted for rescue. Topical corticosteroids are only permitted after the completion of all day 1 activities. After week 2, rescue with any approved AD therapy is allowed, however, study treatment will be discontinued for those subjects who use phototherapy, systemic corticosteroids, or injectable treatments as rescue therapy. Only those subjects using TCS and/or TCI as rescue will be permitted to continue concurrent therapy with study drug.

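### The SAP scores only topical (TCS/TCI) rescue as non-response, so a response reached on stronger rescue counts for the randomized arm: a narrow gap in Part A to week 16, a wider one in the estimation-only Part B.

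*Protocol*

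**What the plan says.** **Rescue in Part A.** Protocol 7.1.5 allows no rescue in the first 4 weeks. After that, "Investigators are to attempt to limit the first step of rescue therapy to topical medications", and they may "escalate to systemic medications only for subjects who do not respond adequately following at least 7 days of topical treatment". Systemic rescue stops study drug. No phototherapy or injectable rescue is foreseen, and 7.1.7 adds "Phototherapy is prohibited during the first 16 weeks of the study".

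**Rescue in Part B.** Once the week 2 activities are done, "subjects may receive rescue treatment with any approved AD therapy" (7.1.5), with no topical-first step. Protocol 7.1.7 repeats the permission: "After week 2, rescue with any approved AD therapy is allowed, however, study treatment will be discontinued for those subjects who use phototherapy", and lists systemic corticosteroids and injectables with it. Its next sentence lets only subjects rescued with TCS and/or TCI stay on study drug.

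**Bans.** Protocol 7.1.7 also says "The use of biologics, including dupilumab, is prohibited while participating in this study", and its sentence on systemic immunosuppressants ends "Ig and or blood product during the study period is prohibited". Neither sentence mentions rescue.

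**Follow-up.** Protocol 7.1.5 and 7.4.2.1 keep rescued subjects on the visit and assessment schedule, so week 16 scores will exist.

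**Scoring.** SAP 2.1 names two intercurrent events: stopping study drug, which is disregarded, and TCS/TCI rescue, which is a non-response. SAP 5.5 codes a response as 1 when the IGA or EASI criterion is met at week 16 and there was no TCS/TCI rescue from day 29. SAP 5.6 carries the rule to the other time points and to Part B. SAP 5.4 discards scores only after TCS/TCI rescue. SAP 9.6.9 lists only TCS and TCI as therapies of interest.

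**The concern.** The rule fails the milder rescue and credits the stronger one, and neither document gives a reason. Because visits continue and stopping drug is disregarded, a subject who did badly on study treatment and cleared on, say, cyclosporine is a success for the arm he or she was randomized to. If stronger rescue is commoner on placebo, the difference is pulled toward zero. If it is equally common, the risk difference holds but the odds ratio, which is the primary summary measure, still shrinks. The SAP 9.6.9 table would not show how many such subjects each arm has. At stake are the size of the Part A primary estimates and the credibility of the Part B estimates.

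**Working it through.** **1. Does any rule catch these subjects?** Take a subject with IGA 0 or 1 at week 16, systemic rescue, and no TCS/TCI from day 29. SAP 5.5's first condition is met, so the endpoint is 1; the fallback to 0 is never reached. SAP 5.4 does not discard the score, and SAP 2.1 disregards the stop of study drug. No other SAP rule for the binary endpoints applies.

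**2. How can it arise?** In Part A, week 4 is day 29 (4 × 7 + 1), so topical rescue given when first allowed already falls in the scoring window. A subject who follows the ladder with TCS/TCI is scored 0 before any systemic drug. Only systemic rescue without TCS/TCI escapes, and that is possible because investigators need only attempt topicals first. In Part B rescue opens after week 2 (day 15) with no ladder, so any of the stronger classes can come first.

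**3. The plan's own Part B figure.** SAP 3.2 gives a 95% CI half-width of about 20% for a 30-point IGA 0/1 difference. With 40 active and 20 placebo, and the Part A planning rates of 40% and 10% borrowed for Part B (an assumption): 1.96 × √(0.40 × 0.60/40 + 0.10 × 0.90/20) = 1.96 × 0.1025 = 20.1 points. Reproduced.

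**4. Part B, IGA 0/1, with extra responders on stronger rescue.** The documents give no rescue rates, so the counts are assumptions. Same Wald formula:

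| Extra responders | Active | Placebo | Difference, points (95% CI) |
|---|---|---|---|
| none | 16/40 | 2/20 | 30.0 (9.9 to 50.1) |
| 1 placebo | 16/40 | 3/20 | 25.0 (3.2 to 46.8) |
| 2 placebo | 16/40 | 4/20 | 20.0 (-3.2 to 43.2) |
| 1 active | 17/40 | 2/20 | 32.5 (12.3 to 52.7) |
| 2 active, 1 placebo (5% each) | 18/40 | 3/20 | 30.0 (8.0 to 52.0) |

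Per subject: 1/20 = 5.0 points on placebo, 1/40 = 2.5 points on active.

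**5. Part A, IGA 0/1, 60 per arm at the planning rates** (24 and 6 responders). Unadjusted odds ratio = a(60 − b)/[(60 − a)b], where a is active and b placebo; Pearson chi-square without correction:

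| Extra responders | Active v placebo | Odds ratio | p |
|---|---|---|---|
| none | 24 v 6 | 1296/216 = 6.00 | 0.00015 |
| 1 placebo | 24 v 7 | 1272/252 = 5.05 | 0.00039 |
| 1 active | 25 v 6 | 1350/210 = 6.43 | 0.00007 |
| 1 in each arm | 25 v 7 | 1325/245 = 5.41 | 0.00020 |
| 3 in each arm | 27 v 9 | 1377/297 = 4.64 | 0.00034 |
| 3 placebo | 24 v 9 | 1224/324 = 3.78 | 0.0022 |

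The target odds ratio in SAP 5.4 is 5.29. Every p-value is below 0.025. For EASI 75 (30 v 9) the odds ratio is 5.67; one extra in each arm gives 5.34, three in each 4.89.

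**6. Part A power.** The normal-approximation chi-square formula with 54 evaluable per arm and two-sided 0.025 gives 92.6% for 10% v 40%, consistent with the stated floor of 85%. If 2.5% or 5% of placebo subjects, and none on active, became responders this way, power would be 85.5% or 75.7%. These shares are assumptions too, and the ladder makes the larger one hard to credit.

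**The case against.** The strongest defence is that the scoring follows a stated framework. SAP 2.1 speaks of concurrent use of TCS/TCI, and Protocol 7.1.7 reserves concurrent therapy for those same topicals. On this reading, rescue alongside study drug is a failure, whereas stronger rescue means stopping drug, which the estimand disregards; Protocol 8.1 wants such subjects kept on study for outcome data. This probably explains how the text arose. It does not explain why failing the milder rescue and crediting the stronger one would be wanted.

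Other objections stand and limit the point:

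- **Part A.** A reader might infer that the primary test is at risk. The documents do not support that: rescue is barred for 4 weeks, systemics normally follow at least 7 days of topicals, and phototherapy is banned to week 16. The counts above are extra responders who meet every condition, not rescue users.
- **Conflict within 7.1.7.** A reader might infer that sites are left without a stop rule. In Part B the sentence limiting continued study drug to TCS/TCI rescue covers every other class, and Protocol 8.1 stops study drug for systemic rescue. The Part B paragraph reads naturally as a specific exception to the general bans.
- **Time to EASI response.** SAP 9.5.2 censors at rescue medication without naming TCS/TCI. A reader might infer a deliberately broader rule. It may equally be shorthand for the phrase used elsewhere in the SAP, so it proves no inconsistency.
- **Part B.** SAP 5.6 refers to the use of TCS/TCI. If that includes regimen TCS, TCS users are already non-responders and the gap largely closes. Protocol 7.1.5 suggests otherwise, since it reserves the word for stronger topicals ("subjects may be treated (rescued) with high or super-high potency TCS, unless higher potency TCS is considered unsafe"), but the SAP does not say so.

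**Conclusion.** The concern holds as a minor scoring gap. As written, a response at the assessment reached on systemic, phototherapy or injectable rescue without countable TCS/TCI is credited to the randomized arm.

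- **Part A to week 16:** narrow, limited to systemic rescue given without TCS/TCI. In the assumed cases the IGA 0/1 odds ratio ranges from 3.78 to 6.43 against 6.00, and no test decision changes.
- **Part B:** wider, because any approved therapy is open after week 2 with no topical-first step. One such responder moves the difference by 5 points (placebo) or 2.5 points (active), within a confidence interval about 40 points wide. Part B tests no hypothesis, so this is a matter of estimation.

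This rests on assumed counts, on planning rates borrowed from Part A for Part B, and on regimen TCS not counting as rescue. The missing exception sentence in Protocol 7.1.7, and whether injectable treatments include biologics, are points of clarification and not errors of design.

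**What to change.** 1. **SAP 5.5 and 5.6.** Add as the first derivation rule: code the response as 0 if the subject received a systemic corticosteroid, a systemic immunosuppressant, phototherapy or an injectable treatment as AD rescue at any time from first dose to the assessment. Apply it at every time point in both parts.
2. **SAP 5.6, Part B.** State that TCS used under the Protocol 7.1.5 regimen is not rescue, while high or super-high potency TCS and TCI are.
3. **SAP 2.1 and 5.4.** Add the same classes to the intercurrent events and to the rules for discarding scores, so that estimand, binary endpoints and continuous endpoints agree.
4. **SAP 9.6.9.** Add the four classes to the therapies of interest.
5. If Part A is already unblinded, run the rule there as a sensitivity analysis only.
6. **Clarification in Protocol 7.1.7:** say that the bans yield to rescue only where 7.1.5 or the Part B paragraph allows it, with study drug stopped, and say whether injectable treatments include biologics. Keep the biologic ban unless the sponsor decides otherwise.

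The cost is a handful of SAP edits and a small departure from treatment policy for subjects who stop drug because of stronger rescue. Protocol 7.8.2 already collects concomitant therapies with names and dates, so no new data, visits or subjects are needed.

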7.2 Method of Treatment Assignment

In Part A, subjects will be randomized in a 1:1:1:1 allocation ratio, to tezepelumab 420 mg SC Q2W, 280 mg SC Q2W, 210 mg SC Q4W, or placebo, respectively, in double-blind manner.

In Part B, subjects will be randomized in a 2:1 allocation ratio to 420 mg SC Q2W or placebo, respectively, in a double-blind manner.

The randomization will be performed by IVRS/IWRS.

The randomization date is to be documented in the subject's medical record and on the enrollment case report form.

7.3 Blinding

Both Part A and Part B of this study are double-blind. Treatment assignment will be blinded to all subjects, study center personnel, and Amgen as described below.

7.3.1 Study Center Personnel Access to Individual Treatment Assignments

A subject's treatment assignment is to only be unblinded when knowledge of the treatment is essential for further clinical management of the subject on this study. Unblinding at the study center for any other reason will be considered a protocol deviation. The Amgen Trial Manager must be notified before the blind is broken unless identification of the study treatment is required for a medical emergency in which the knowledge of the specific blinded study treatment will affect the immediate management of the subject's condition. In this case, the Amgen Trial Manager must be notified within 24 hours after breaking the blind. The date and reason that the blind was broken must be recorded in the source documentation and CRF, as applicable.

A description of how responsible pharmacists and investigators will access treatment information (eg, via the IVR/IWR system), in the event that there is a need to break the blind, will be detailed in the IPIM.

7.3.2 Access to Individual Subject Treatment Assignments by Amgen or Designees

Blinded individuals will not have access to unblinded information until the study is formally unblinded. Unblinding and potentially unblinding information is not to be distributed to the study team, investigators or subjects prior to the study being formally unblinded except as specified (eg, [Section 7.3.1](#)).

Staff from Clinical Supply Chain, Biological Sample Management, Clinical Pharmacology Modeling and Simulation, Computational Biology, Clinical Immunology, Clinical Biomarkers and Diagnostics, and Global Biostatistical Sciences departments who are responsible for tracking, assaying, or analyzing biological samples during the conduct of this study are considered unblinded to the treatment assignments in this study. These individuals will not to have access to subject level clinical data apart from the samples they are assaying and analyzing during the course of the study.

If exposure-response analysis is performed, the exposure-response analysis team, including Clinical Pharmacology Modeling and Simulation and Global Biostatistics

Sciences, who are independent of the study team, may be unblinded. The analysis plan and data integrity document for the exposure-response analysis will detail the analyses and describe the timing for unblinding according to Amgen's standard operating procedure.

7.4 Dose Modification

In Part A of this study, subjects who are determined to be non-responders will receive tezepelumab 420 mg SC Q2W for the remainder of the study, beginning with the week 18 dose. Non-responders are defined as those subjects who have not achieved at least a 50% improvement in EASI at week 16 compared to baseline (day 1). The randomized treatment assignments for the non-responders will remain blinded until the end of study.

In Part B, there will be no dose modification.

7.4.1 Dose-cohort Study Escalation/De-escalation and Stopping Rules

Not applicable.

7.4.2 Dosage Adjustments, Delays, Rules for Withholding or Restarting, Permanent Discontinuation

7.4.2.1 Amgen Investigational Product: Tezepelumab

The reason for dose change of tezepelumab is to be recorded on each subject's CRF(s).

An individual subject may be discontinued at the discretion of the investigator and/or the sponsor due to clinically significant events.

In Part A of the study, subjects who are determined to be non-responders will receive tezepelumab 420 mg SC Q2W for the remainder of the study, beginning with the week 18 dose. Non-responders are defined as those subjects who have not achieved at least a 50% improvement in EASI at week 16 compared to baseline (day 1). The randomized treatment assignments for the non-responders will remain blinded until the end of study.

Subjects who receive rescue therapy with topical medications may continue treatment with study drug, per the instructions outlined in [Section 7.1.5](#).

If a subject receives rescue treatment with systemic corticosteroids or nonsteroidal systemic immunosuppressive drugs (eg, cyclosporine, mycophenolate-mofetil, azathioprine), study treatment is to be immediately discontinued. All subjects are to complete the schedule of study visits and assessments whether or not they complete study treatment or receive rescue treatment for AD.

7.4.2.2 Non-Amgen/Amgen Non-Investigational Products

7.4.2.2.1 Topical Corticosteroids

Topical corticosteroid use is prohibited in Part A of this study. If topical corticosteroid use is required during Part A, refer to rescue guidance in [Section 7.1.5](#).

In Part B of this study, subjects are allowed to initiate TCS use following completion of all day 1 activities. Subjects who apply TCS are to follow the dosing regimen described in [Section 7.1.5](#).

Subjects will be monitored for signs of local or systemic TCS toxicity and will step down or stop treatment as directed by the Principal Investigator, who should direct the type and length of therapy. Signs of local toxicity include skin thinning; signs of systemic toxicity include hyperglycemia.

The reason for dose change of TCS is to be recorded on each subject's CRF(s).

